#### **14.2 Prohibited Concomitant Therapy**

Except for the investigational and reference drugs, no other cytoreductive (i.e., leading to decrease of cell counts in peripheral blood) therapy, JAK inhibitors, nor any other drugs leading to a decrease of peripheral blood cell counts are allowed in this study. Investigational medications, other than the study drugs used in this study, are not allowed in this study.

In addition, interstitial pneumonitis associated with the concomitant use of interferon- $\alpha$  preparations and Sho-sai-ko-to (or xiao-chai-hu-tang, herbal medicine) has been reported as safety data common to interferon- $\alpha$  2a and interferon- $\alpha$  2b products. Therefore, the concomitant use of Sho-sai-ko-to is contraindicated from a safety standpoint.

The contraindicated concomitant therapy period is set as from obtaining informed consent to the safety follow-up visit after completion of the administration period.

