### **Investigational Product and Reference Therapy, Dosage, and Mode of Administration:**

Patients who meet the inclusion criteria and who do not meet the exclusion criteria will start therapy with P1101 (ropginterferon alfa-2b). The investigational product will be administered subcutaneously every 2 weeks at the starting dose of 100 µg every two weeks (or 50 micrograms in patients under another cytoreductive therapy). The dose should be gradually increased by 50 µg every two weeks (in parallel, other cytoreductive therapy should be decreased gradually, as appropriate) until stabilization of the hematological parameters is achieved (hematocrit <45%, platelets <400 x 10^9/L and leukocytes <10 x 10^9/L). The maximum recommended single dose is 500 µg injected every two weeks. The dose will be maintained at the highest level which can be tolerated and delivers best possible disease response.

Low-dose aspirin (acetylsalicylic acid) (75-150 mg/day per local practice) will be given during the 12 months of study treatment, unless contraindicated.

Phlebotomy is performed aiming at a hematocrit < 45%. When the hematocrit value is 45% or higher, phlebotomy is performed. The volume of phlebotomy per procedure should be 200 to 400 mL per one phlebotomy while monitoring the circulatory dynamics such as blood pressure and pulse. In the elderly and patients with cardiovascular disorders, a small volume (100 to 200 mL) should be considered to avoid rapid changes in hemodynamics.

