### 12.5 Dosage and Dosing Schedule

P1101 will be administered SC during the study visits every 2 weeks. Subjects will receive an initial dose of 100 µg at Week 0, 150 µg at Week 2, and then 200 µg at Week 4, etc., i.e. dose escalation by 50 µg biweekly until 500 µg, or until response will be achieved. The dose can be further adjusted to prior dose for safety and tolerability reasons, but should preferably remain fixed for the treatment period.

The study drug should be administered SC into the abdominal skin around but not within 5 cm of the navel. If the abdomen appears inappropriate or unfavorable for injection according to the Investigator's judgment, study drug can be injected SC into the thigh. At the time of dispensing, the person administering the study drug will note the date and time of administration, both of which are then to be documented into the subject's eCRF.

A standardized dosing paradigm will be used to determine dose adjustments for safety and tolerability so that each subject will receive their most appropriate dose (Section 12.5.2).

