## **24.7 Appendix 7. Transition phase from previous HU treatment to P1101 (for all patients on active HU)**

Transition phase is the initial part of the dose finding for the patients concurrently receiving HU at the time of screening but transferred to P1101.

The following scheme will be applied:

	HU weekly dose	P1101 dose
Week 1-2	100% of the dose at baseline	50 mcg
Week 3-12 Earliest possible HU discontinuation is being encouraged	Every two weeks, decrease the HU level 250-500 mg	Every two weeks, increase the P1101 level by 50 mcg
By week 13 onwards	discontinued	Monotherapy with dose, allowing CHR

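### For patients on cytoreductive therapy at entry, the protocol's prohibition, start-dose and hydroxyurea-taper passages do not agree with one another

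*Protocol*

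**What the plan says.** **Prohibition.** Protocol Section 14.2 opens: "Except for the investigational and reference drugs, no other cytoreductive (i.e., leading to decrease of cell counts in peripheral blood) therapy, JAK inhibitors" and other count-lowering drugs are permitted. The section closes with the period: "The contraindicated concomitant therapy period is set as from obtaining informed consent to the safety follow-up visit after completion of the administration period". Between the two stands a paragraph on the herbal medicine Sho-sai-ko-to. Section 14.1, on allowed therapy, does not list HU.

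**Transition.** Appendix 7 defines its scope: "Transition phase is the initial part of the dose finding for the patients concurrently receiving HU at the time of screening but transferred to P1101". In Weeks 1–2 HU stays at "100% of the dose at baseline". In Weeks 3–12 the instruction is "Every two weeks, decrease the HU level 250-500 mg", with early stopping encouraged, and a last row has HU discontinued from Week 13. The column is headed "HU weekly dose". The synopsis and SAP Section 2.1 likewise have other cytoreductive therapy reduced gradually while P1101 is increased.

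**Start dose.** Section 12.5: "Subjects will receive an initial dose of 100" µg at Week 0, with no exception and no pointer to Appendix 7. Section 12.1 also gives 100 µg but then refers patients on active HU to Appendix 7, which gives 50 µg. The synopsis gives 100 µg "or 50 micrograms in patients under another cytoreductive therapy", and SAP Section 2.1 has the same rule.

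**The concern.** Appendix 7 exists because patients on HU are expected, so these instructions will be used. A site that follows Section 14.2 and a site that follows Appendix 7 would treat the same patient differently, and a patient treated exactly as Appendix 7 directs is on therapy that Section 14.2 does not allow.

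This is first a matter of safety and uniform conduct, but it also reaches the data:

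- SAP Section 3.4 takes baseline as the last value before the first dose. If sites differ on HU during the screening period of up to 28 days, baseline counts do not mean the same thing at every site, and the change-from-baseline endpoints inherit that.
- HU may run through Week 12, so up to about the Month 3 visit. That visit feeds the response-over-time summary and its slope (SAP Section 4.3.5.2).
- Protocol deviations are graded major or minor case by case, and a major one removes the patient from the per-protocol population. With 30 patients planned, a few such decisions could be visible.

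**Working it through.** **1. Prohibition against transition.** The only exemption in Section 14.2 is for investigational and reference drugs. The study is single-arm, Table 12-1 lists P1101 alone, and no passage names HU as a reference drug. The exemption therefore does not reach HU on the page, and nothing in Section 14.2 or 14.1 refers to Appendix 7. The two cannot both be followed in Weeks 1–12.

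**2. Start dose, place by place.**

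| Place | Patient on HU | Patient on another cytoreductive drug |
|---|---|---|
| Synopsis; SAP 2.1 | 50 µg | 50 µg |
| Section 12.1 | 50 µg (by pointer to Appendix 7) | 100 µg |
| Section 12.5 | 100 µg | 100 µg |
| Appendix 7 | 50 µg | not covered |

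For HU, Section 12.5 is the only outlier. For other cytoreductive drugs, both body sections differ from the synopsis and SAP, and there is no transition scheme. Where places differ, the factor is 100/50 = 2.

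**3. Taper.** The plan's own figure is zero HU from Week 13. It can be neither reproduced nor refuted from the steps, because the documents give no baseline HU dose.

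- Steps: one every two weeks in Weeks 3–12, at Weeks 3, 5, 7, 9 and 11, so 5 steps.
- Total cut: 5 × 250 = 1,250 mg to 5 × 500 = 2,500 mg.
- Read as mg per week, the steps reach zero only from a baseline of at most 1,250–2,500 mg/week. That is 1,250/7 ≈ 179 to 2,500/7 ≈ 357 mg/day.
- Read as mg per day, they reach zero from a baseline of up to 1,250–2,500 mg/day.

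Remaining dose = max(0, baseline − cut), for assumed baselines. The only HU dose in the documents is the 2 g/day resistance threshold in Appendix 6, which is not an entry dose.

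| Assumed baseline | Per week | Left after 5 steps, weekly reading | Left after 5 steps, daily reading |
|---|---|---|---|
| 250 mg/day | 1,750 mg | 0–500 mg/week | 0 |
| 500 mg/day | 3,500 mg | 1,000–2,250 mg/week | 0 |
| 1,000 mg/day | 7,000 mg | 4,500–5,750 mg/week | 0 |
| 2,000 mg/day | 14,000 mg | 11,500–12,750 mg/week | 0–750 mg/day |

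Counting a sixth step at Week 13 makes the cut 1,500–3,000 mg; on the weekly reading an assumed 500 mg/day still leaves 500–2,000 mg/week. Under the weekly reading, then, the steps take off 1,250/3,500 = 36% to 2,500/3,500 = 71% of an assumed 500 mg/day, and the Week 13 row removes the rest in one drop. The two readings differ by a factor of 7.

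**4. Distance from the primary endpoint.** HU ends by Week 13 and the first primary assessment is at Week 36, 36 − 13 = 23 weeks later. A look-back of 3 months (about 13 weeks) starts near Week 23, some 10 weeks after HU has ended.

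**The case against.** The strongest reply is that the specific rule governs the general one. Appendix 7 is explicit about patients on HU at screening, Section 12.1 sends them there, and a careful site would not start such a patient at 100 µg. For HU this has force: the start-dose conflict comes down to one section that lacks a cross-reference. It does not help patients on other cytoreductive drugs, whom Appendix 7 does not cover.

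Second, the period sentence in Section 14.2 directly follows the Sho-sai-ko-to paragraph and shares its term for contraindicated use, so it may govern only that product. This stands as a limit. A reader might infer that sites must stop HU up to four weeks before P1101, but the documents do not establish that. The opening sentence of Section 14.2 still bars other cytoreduction in the study, whatever the period sentence covers.

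Third, a reader might infer that the taper cannot reach zero by Week 13. The documents do not support this. Low weekly doses do reach zero, earlier stopping is encouraged, and the last row ends HU under either unit. Nor does the daily reading always close the gap: 250 mg steps from an assumed 2,000 mg/day leave 750 mg/day. What remains is an unclear unit that decides between a gradual taper and an abrupt end.

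Fourth, prohibited concomitant therapy is not among the listed deviations in Protocol Section 17.3.4 or SAP Section 4.2, and the per-protocol population serves sensitivity analysis only. That is correct. Other observations may be considered, so an effect is possible, but none is shown.

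**Conclusion.** The concern holds as an internal inconsistency in three parts:

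- Section 14.2 states no transition exception, while Appendix 7, the synopsis and SAP Section 2.1 provide for overlap.
- The start dose differs two-fold, in Section 12.5 for patients on HU and in Sections 12.1 and 12.5 for patients on other cytoreductive drugs.
- The unit of the Appendix 7 taper is open to a sevenfold difference in reading.

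The first two rest on the text alone. The five-step count and the thresholds of 1.25–2.5 g follow from Appendix 7; the remaining-dose figures rest on assumed baselines.

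A reader might go further and infer damage to the primary result. The documents do not show it, since HU is to end by Week 13 and the primary assessments are at Weeks 36 and 52. Nothing here says which dose, unit or rule is right. The point should be corrected because it bears on patient safety and uniform conduct and is cheap to settle.

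**What to change.** Reconcile the synopsis, Protocol Sections 12.1, 12.5 and 14.2, Appendix 7 and SAP Section 2.1 so that:

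- Section 14.2 and the transition scheme agree. Section 14.2 should say how its ban applies to patients on HU or other cytoreduction at entry, which therapies the period sentence covers, and what the term for reference drugs means in this trial, or drop it.
- One start-dose rule appears in the same words, or by cross-reference, everywhere it is stated, and covers both HU and other cytoreductive drugs.
- Appendix 7 states whether the taper amounts are per day or per week, consistently with its column heading and its Week 13 row.

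The clinical values are for the sponsor to decide. The cost is a protocol clarification and, if the start rule changes, a matching line in the SAP. Sample size and the primary analysis are untouched.

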#### **14.3 Contraception Use**

Females of childbearing potential will be required to use oral, injectable, or implanted contraceptives. Use of hormonal contraception will be determined by the Investigator, taking into account the therapy used, the manufacturer's instructions, labeling, and accepted medical practice.

Male subjects will use an appropriate method of contraception, such as vasectomy (confirmed to be azoospermia) or condom use.

In this study, contraception is required from the start of the study to 28 days after the last dose of the investigational product, regardless of gender.

## 15 STUDY EVALUATIONS

### 15.1 Study Procedures by Visit

#### 15.1.1 Overview

The study is divided into 2 phases with associated evaluations and procedures that must be performed at specific time points, as described in the following sections. The study flowchart (Appendix 1) summarizes the frequency and timing of study events.

As soon as the subject is considered for this study, and prior to any other study procedures, the subject will have the nature of the study explained to them, and will be asked to give written informed consent. Informed consent must be obtained prior to any procedures during the course of a clinical trial.

Subjects who are prematurely discontinued from the study should attend the safety follow-up visit 28 days after the last study drug administration.

#### 15.1.2 Screening (-28 days/-1 day)

Subjects who might meet the inclusion criteria will be contacted and asked for their interest in participating in the study. If they agree to participate in the study, all subjects must provide written informed consent before any study-specific assessments or procedures are performed.

Subjects who are considered for study entry but fail to meet one or more of the eligibility criteria should not be reported in the eCRF. A detailed reason for ineligibility should be reported in the screening log.

An eCRF should be completed for all subjects fulfilling all of the entry criteria.

The site notifies the Sponsor when a subject eligible according to all inclusion and exclusion criteria is to be enrolled into the study. Study entry (enrollment) is defined by the subject's, or their legally authorized representative's, signature on the informed consent form. All subjects enrolled will be assigned a subject ID number.

The following assessments will be completed according to the study flowchart (Appendix 1).

- Informed consent - verification of personally signed and dated informed consent of the subject, or their legally authorized representative, prior to any study-related examinations performed
- Inclusion and exclusion criteria - Subjects who meet all inclusion criteria and none of the exclusion criteria will be invited to participate in the study
- Demographic information (e.g., age, sex, and race) will be recorded at screening in the appropriate eCRF. Relevant medical history, including history of prior and current disease(s), and information regarding underlying diseases will also be recorded at screening. Included will be the usage of any and all drugs used to treat PV.
- Standard 12-lead ECG
- A urine pregnancy test must be performed within 7 days prior to the first administration of study drug and subsequently every 4 weeks for all women of childbearing potential (no hysterectomy or bilateral oophorectomy, or at least 12 consecutive months without spontaneous menopause [i.e., menstruation occurred sometime in the past 12 consecutive months], or amenorrhea due to medical treatment such as antineoplastic drugs) as well as for all women <2 years from the onset of presumed menopause (the time point of completion of the last menstruation was considered as menopause, when the next menstruation has not started for more than 2 years)
- Complete physical examination
- Vital signs (pulse rate, blood pressure, and body temperature)
- Blood chemistry
- Blood coagulation

- Serology to exclude systemic infections; the tests commonly used in the local setting for diagnosing current infections (with HIV and HCV, as well as hepatitis B surface antigen [HBsAg] to detect HBV infection) are to be performed for eligibility assessment purposes
- Hematology
- Autoimmune markers (blood)
- Urine test
- Urine beta 2 microglobulin test
- ECOG performance status
- Spleen size measurement: Spleen size will be measured by palpation and, for palpable spleen, subsequently by ultrasound with local review of the images
- Genetic test sample including JAK-2 allelic burden (data collected according to WHO criteria)
- Bone marrow sampling (optional). Bone marrow biopsy collected within 6 months of Screening could be used to replace the Screening sample. If a sample was taken within 6 months, but since then the patient was treated with HU and failed, the sample needs to be retaken.
- AEs
- Concomitant treatment
- Ocular examination
- Lung X-ray: Will be accepted if they are not older than 12 weeks prior to the date of the screening visit
- Heart ECHO: Will be accepted if they are not older than 12 weeks prior to the date of the screening visit
- HADS (Appendix 8)
- After having successfully completed the screening period and if found eligible for the study, the subjects will receive the study treatment.

### **15.1.3 Treatment Period Week 0 to Week 52**

The first dose of study drug will be administered at 0 hours on Day 1.

All assessments, including local laboratory samples, are to be completed prior to the study drug administration at each visit.

Note: If hematology and/or blood chemistry are done within 7 days prior to Visit 1, they do not have to be repeated.

Please refer to the study flowchart and others (Appendix 1, Appendix 2, Appendix 3) for specific assessments at each visit.

### **15.1.4 Safety Follow-up or End of Study Visit**

Subjects who discontinue study drug prematurely will return for a follow-up visit 28 days after the last dose. Please refer to the study flowchart and others (Appendix 1, Appendix 2, Appendix 3) for visit-specific assessments.

If subjects will participate in extension study of A19-201, safety follow-up will not be performed.

Subjects who discontinue study drug due to a suspected study drug-related AE must be followed at least once a week for 8 weeks and subsequently at 2-week intervals until resolution or stabilization of the event.

If a subject has not recovered from any toxicity within 8 weeks of prematurely discontinuing study drug, s/he must be discontinued from the study, but will continue to be followed for toxicity as described above.

Subjects who discontinue study drug due to a severe thromboembolic event will have an AE reported as the reason for discontinuation, and “severe thromboembolic event” indicated in the specific field.

If a subject has not recovered from any toxicity within 8 weeks of prematurely discontinuing study drug, s/he must be discontinued from the study, but will continue to be followed for toxicity as described above. In this case, data may not be entered into the database but will be documented in the study log, and stored at the site.

There may be a post-study care opportunity for study subjects who benefit from P1101 therapy. Further details will be provided as a separate protocol or amendment to this protocol at a later stage.

## 15.2 Pharmacokinetic and Immunogenicity Evaluations

### Pharmacokinetic Evaluation

- The PK samples will be collected for population PK analysis of P1101.
- Serial PK samples (n=4 per subject) will be collected at Week 0 and Week 28, at the following time points: pre-dose (0 hr), 48 ( $\pm 24$ ) hr, 96 ( $\pm 24$ ) hr, and 168 ( $\pm 24$ ) hr. At Weeks 0 and 24, subjects must administer their P1101 dose in the clinic.
- Trough PK samples will be collected at every visit.
- The PK sampling schedule is provided in Appendix 2. The actual date and time of dose and PK sample collection must be recorded on the CRF.
- All P1101 treated subjects will have their blood samples collected for the analysis of serum concentrations of P1101 according to the study flowchart (Appendix 1, Appendix 2). Population PK/PD models will be updated with the PK and PD data from Week 0 to Week 12 of the first 15 subjects in the P1101 arm.
- Detailed instructions will be provided in a laboratory manual and stored in the investigator site file.

### Immunogenicity Evaluation

- The immunogenicity samples will be collected for anti-drug antibody assessment for P1101.
- Blood samples will be collected from the subject confirmed positive for P1101 ADA at EoS visit every three months until ADAs return to baseline levels or up to 12 months.
- The immunogenicity sampling schedule is provided in Appendix 3. The actual date and time of dose and immunogenicity sample collection must be recorded on the CRF.
- All P1101 treated subjects will have their blood samples collected for the analysis of serum anti-drug antibody against P1101 according to the study flowchart (Appendix 3).
- Detailed instructions will be provided in a laboratory manual and stored in the investigator site file.

## 15.3 Assessment of Efficacy

### 15.3.1 Efficacy Measurements and Time Points

#### 15.3.1.1 Primary Efficacy Measurements – Peripheral Blood Count Remission

The primary efficacy endpoint is the phlebotomy-free complete hematologic responder rate (CHR) at month 9 and month 12.

The phlebotomy-free responder rate is defined as the proportion of patients with complete hematologic response (CHR) and with no phlebotomies during the previous 3 months.

A responder in sense of a primary endpoint is a patient who has met all of the following criteria at month 9 and month 12:

- • Hematocrit <45% phlebotomy-free (absence of phlebotomy during the previous 3 months)

- • Platelet count  $\leq 400 \times 10^9/L$ ,
- • WBC count  $\leq 10 \times 10^9/L$

Scheduled hematological assessments will occur as indicated in Appendix 1. Samples for hematology assessments will be prepared using standard procedures. For the hematologic parameters of Hct, platelets and WBCs, central laboratory assessments at Weeks 0, 12, 24, 36, and 52 will be used for determination of responder. Detailed specifications for hematology sample handling, shipping, and processing will be provided in a laboratory manual.

### **15.3.1.2 Other Efficacy Measurements**

There will be disease response assessments at Weeks 0, 12, 24, 36, and 52 of treatment with P1101. During these times, changes in Hct, WBC, PLT, spleen size, molecular response from baseline, time to requiring no phlebotomy, numbers of phlebotomy required, time to response, duration of response maintenance, ratio of CHR rates of subjects with/without prior treatment with HU and Proportion of subjects without thrombotic events will be assessed.

### **15.3.1.3 Genetic Assessment of *JAK2***

Genetic assessments will consist of screening tests for PV diagnosis purposes and quantitative *JAK2* measurements at screening, Weeks 0, 12, 24, 36 and 52 (central laboratory). Change of *JAK2* allelic burden over time will be assessed (by ELN 2013 criteria; (Barosi et al. 2013) ).

Whole blood samples, collected from all subjects prior to study drug administration, will be centrally assessed. Detailed instructions for sample handling, labeling, and storage will be provided in the laboratory manual.

Handling of samples for *JAK2* mutation assessment and disclosure of assay results to subjects are as follows.

- Storage period, storage method and disposal of samples

DNA samples are extracted from whole blood at a central laboratory and stored in a locked and manageable refrigerator.

The DNA samples are handed over to the company handing industrial waste as industrial wastes 6 months after the end of the determination.

- Volume of blood samples collected

Three mL of whole blood is collected from vein at each sampling

- Disclosure plan of genetic test results to subjects and the reason

The genetic test results will be disclosed to the subject or the subject's legally acceptable representative, only if the subject or the subject's legally acceptable representative desire to know the results.

- Handling of blood samples if the consent is withdrawn the use of blood samples during the study

If a subject withdraws consent to the genetic mutation test during the study period, the genetic test will be discontinued, and the sample will be discarded.

